### **10.3. Analysis Methods**

The number of patients in all study populations, as well as the distribution by site will be presented. The reasons for interruption of patient follow-up will be listed and the average time of patient follow-up will be given. Descriptive statistical data will be used to summarize the characteristics of subjects at the time of inclusion (demographics, baseline and procedure data).

Quantitative parameters will be described using the following summary descriptive statistics at each time point: number of non-missing values, mean, standard deviation, median, first and third quartiles, and minimum and maximum values. Qualitative parameters will be described overall using frequencies and percentages. Percentages will be calculated on the number of non-missing observations. In order to provide unbiased and informative findings, no replacement of missing values is planned for any parameters. In all applicable cases, reported analysis will mention the number of missing values for each outcome relatively to the considered analysis set.

Analysis of safety will be performed on the ITT population and the As-Treated population. The primary safety endpoint will be analyzed using a unilateral one sample test for binomial proportion at the 5% level. In addition, the exact bilateral 95% confidence interval will also be given. The statistical test for the primary safety endpoint is given by:

- H0: M-Trap freedom MAE incidence  $\leq$  90% - Non inferiority margin (25%)  
Versus
- HA: M-Trap freedom MAE incidence  $>$  90% - Non inferiority margin (25%)

The primary performance endpoint is the percentage of recurrent patients with histological evidence of tumor cell capture in at least one M-Trap device. The secondary performance endpoints are the percentages of recurrent patients with disease focalization scores of: 1) I, 2) I or II, 3) I, II or III, and 4) I, II, III or IV. Analysis of performance will be performed on the As-Treated population. The primary performance and secondary endpoints will be assessed with exact one-sided 90% confidence intervals.

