1. OVERVIEW

This statistical analysis plan (SAP) describes the planned statistical analyses of the data collected in the course of the clinical study of the M-Trap device.

This SAP provides additional details concerning the statistical analyses outlined in the protocol (version 3.0 dated 12 September 2017). The purpose of the SAP is to ensure the credibility of the study findings by pre-specifying the statistical approaches to the analysis of study data.

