2.4.5. Primary Analysis

Primary analysis of safety will be performed on the ITT population and the As-Treated populations.

The primary safety endpoint is freedom from device and procedure-related major adverse events through 6-months post-implantation, including shock, cardiac arrest, myocardial infarction, pulmonary embolism, prolonged intubation, unplanned reintubation, or adverse events leading to removal of the device, including infection, seroma formation, mesh migration, bowel obstruction, adhesions, and local cancer progression through the abdominal wall at M-Trap suture sites.

The primary safety endpoint will be analyzed using a unilateral one sample test for binomial proportion at the 5% level. In addition, the exact bilateral 95% confidence interval will also be given. The statistical test for the primary safety endpoint is given by:

- H0: M-Trap freedom MAE incidence \leq 90% - Non-inferiority margin (25%)
- Versus
- HA: M-Trap freedom MAE incidence $>$ 90% - Non-inferiority margin (25%)

A modified primary analysis will also be performed that uses a freedom from MAE incidence rate that is adjusted for the surgical complexity of the study population, as compared to the Patankar study population, which is the basis of the statistical rationale for this study (repeated in the table below). The total number of extended procedures will be split in four classes: 0, 1, 2, 3 and more.

Procedures	0	1	2	3 or more	AVG
Total patients	1352	1214	254	50	2870
Severe complications, n	51	92	44	9	196
Severe complications, %	3.8%	7.6%	17.3%	18.0%	6.8%

A further modified primary analysis will also be performed that only includes procedure-related events through 30 days, as this is the comparable population to the Patankar study population, which is the basis of the statistical rationale for this study.

Primary analysis of performance will be performed on the As-Treated population and by device location. This analysis will be also performed using these 3 following sub-populations: (1) platinum resistant, recurrent patients; (2) platinum sensitive, recurrent patients; (3) non-recurrent patients (see definition in part 2.5).

The primary performance endpoint is histopathologic evidence of tumor cell capture (see 2.5). Histopathology will be performed after device explant.

The primary performance endpoint will be assessed with exact one-sided 90% confidence intervals.

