2.4.6. Secondary analysis

Secondary analysis of safety will be performed on the ITT population and the As-Treated populations.

STATISTICAL ANALYSIS PLAN

Secondary safety endpoints include incidence of other device-related adverse events and all other adverse events long-term. Patients will be evaluated by physical examination, CT scan, ultrasound, and biomarker cancer antigen CA-125.

A medical coding will be done on the adverse events using the MedDRA dictionary. All adverse events (AEs) will be categorized by system organ class (SOC) and preferred term (PT). A complete description will be done for the following AEs:

- Total number of AEs/SAEs and corresponding number and percentage of patients
- Total number of device-related AEs/SAEs and corresponding number and percentage of patients
- Total number of unanticipated device-related AEs/SAEs and corresponding number and percentage of patients
- Total number of procedure-related AEs/SAEs and corresponding number and percentage of patients
- Total number of device deficiencies and corresponding number and percentage of patients
- The overall mortality rate will also be presented

Secondary analysis of performance will be performed on the As-Treated population.

Secondary performance endpoints include semi-quantitative scoring of disease focalization based on direct visual assessment, CT scan and ultrasound at the time of device removal. In addition, a microscopic assessment will be performed during explant, including cytological assessment of any ascites present, cytological assessment of peritoneal washings, if indicated, and a minimum of two (2) peritoneal biopsies from designated locations, if indicated.

The secondary performance endpoints are the percentages of recurrent patients with disease focalization scores of: 1) I, 2) I or II, 3) I, II or III, and 4) I, II, III or IV. This analysis will be also performed using the 3 sub-populations defined below ((1), (2), (3)), and using the populations (1) and (2) combined and overall.

The secondary performance endpoints will be assessed with exact one-sided 90% confidence intervals.

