2.4.7. Device Removal

Descriptive statistical data will be used to draw up a recapitulation of the device removal details at the time of the removal operation.

The following data will be presented on the As-Treated population on patients number:

- Duration until device removal (days), Reason for removal, All devices removed (Yes/No), The number of devices removed if No. Duration until device removal (days) if the reason for removal is recurrence.
- The time to recurrence will be described using a Kaplan Meier curve. Patients lost to follow-up before the removal will be censored at the date of last follow-up. Patients who have removal for another reason than recurrence before the 18 months will be censored at the date of the removal.
- Disease Focalization: Disease focalization score, Modalities used for the assessment of disease focalization, If a peritoneal wash performed, were malignant cells present (Yes/No)
Disease Focalization will be also analyzed using the 3 sub-populations defined below ((1), (2), (3)), and using the populations (1) and (2) combined and overall.
- Adverse Event: New adverse event(s) occur during removal procedure (Yes/No)
- Cytology (Done with final device removal): Where ascites present (Yes/No), Were malignant cells present in the ascites (Yes/No), Was a peritoneal wash performed (Yes/No), From which area was the wash obtained if "Yes", Were malignant cells present in the peritoneal wash.

	STATISTICAL ANALYSIS PLAN	MTRAP_SAP_v2.0_FINAL redacted.docx
		MTRAP Page 14/15

- Biopsies (Done with final device removal): Biopsy location, Biopsy taken (Yes/No), Is visible tumor present (Yes/No), Is microscopic disease present (Yes/No)

If Biopsy location is Adhesive bands, abnormally scarred areas or Retroperitoneum the further details given will be described by the mean of listing.

The following data will be presented on the As-Treated population on devices number:

- Location of Device, Attachment of the device to the surrounding tissues
- Assessment of device removal: Ease of locating M-Trap device, Did the M-Trap device remain securely fixed in its original location, Ease of removing M-Trap device, Endobag used, Trocar size (mm)
- Core Lab: Device(s) sent to the core laboratory (Yes/No), the Reasons and the Location if No

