- Histopathologic evidence of tumor cell capture is “Yes” if Tumor cell infiltration for at least one device is >0 in a patient. Otherwise, Histopathological evidence of tumor cell capture is “No”.
- An AE will be considered as an SAE if “Serious Adverse event” = “Yes”.
- An AE will be considered “Unanticipated” if “Anticipated adverse event” = “No”.
- An AE will be considered as device related if “Relationship to device(s)” is “possible”, “probable” or “definite”.
- An AE will be considered as procedure related if “Relationship to procedure” is “possible”, “probable” or “definite”.
- At least one other medical history will be calculated as follows:

If at least one variable of other medical history is equal to “Yes” then “At least one other medical history” = “Yes”,

If no variable of other medical history is equal to “Yes” then:

- If all variables of other medical history are equal to “No” then “At least one other medical history” = “No”,
- If at least one variable of other medical history is equal to “Missing” then “At least one other medical history” = “Missing”,

If all variables of other medical history are equal to “Missing” then “At least one other medical history” = “Missing”.

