Table 55: Non-inferiority on Freedom of device and procedure related MAE through 6-months on AT population (Type 5)

Table 56: Freedom of device and procedure related MAE through 6-months on AT population using MAE expected incidence adjusted for the study population number of extended procedures (Patankar definition) (Type 8)

Table 57: Freedom of device and procedure related MAE through 30 days on AT population using MAE expected incidence adjusted for the study population number of extended procedures (Patankar definition) (Type 5)

Primary Performance analysis

Table 58: Histological evidence of tumor cell capture in at least one M-Trap device after device explant on AT population by device location (Type 2)

Table 59: Histological evidence of tumor cell capture in at least one M-Trap device after device explant on AT population with sub-analysis of histological evidence of tumor cell capture by device location and recurrence status (Type 2)

Secondary Analysis

Secondary Safety analysis

Table 60: AEs on ITT population (Type 6)

Table 61: AEs on AT population (Type 6)

Table 62: SAEs on ITT population (Type 6)

	STATISTICAL ANALYSIS PLAN	MTRAP_SAP_v2.0_FINAL redacted.docx
		MTRAP Page 19/20

Table 63: SAEs on AT population (Type 6)
 Table 64: M-trap device related AEs on ITT population (Type 6)
 Table 65: M-trap device related AEs on AT population (Type 6)
 Table 66: M-trap device related SAEs on ITT population (Type 6)
 Table 67: M-trap device related SAEs on AT population (Type 6)
 Table 68: Unanticipated M-trap device related AEs on ITT population (Type 6)
 Table 69: Unanticipated M-trap device related AEs on AT population (Type 6)
 Table 70: Unanticipated M-trap device related SAEs on ITT population (Type 6)
 Table 71: Unanticipated M-trap device related SAEs on AT population (Type 6)
 Table 72: M-trap procedure related AEs on ITT population (Type 6)
 Table 73: M-trap procedure related AEs on AT population (Type 6)
 Table 74: M-trap procedure related SAEs on ITT population (Type 6)
 Table 75: M-trap procedure related SAEs on AT population (Type 6)
 Table 76: Device deficiencies on ITT population (Type 5)
 Table 77: Device deficiencies on AT population (Type 5)
 Table 78: Mortality rate on ITT population (Type 5)
 Table 79: Mortality rate on AT population (Type 5)

Secondary performance analysis

Table 80: Disease focalization scores of I on AT population (Type 5)
 Table 81: Disease focalization scores of I or II on AT population (Type 5)

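### The primary tumor-cell-capture rate is defined among recurrent patients in Protocol 10.3 but analysed on all As-Treated patients in SAP 2.4.5, which does not list the combined recurrent group for capture

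*SAP*

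**What the plan says.** Protocol 10.3 (Analysis Methods) is explicit about the denominator: "The primary performance endpoint is the percentage of recurrent patients with histological evidence of tumor cell capture in at least one M-Trap device". It analyses performance on the As-Treated population with exact one-sided 90% confidence intervals. The Protocol synopsis and section 4.1.2 name the endpoint but give no denominator.

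SAP 2.4.5 reads: "Primary analysis of performance will be performed on the As-Treated population and by device location". It then lists three sub-populations: (1) platinum-resistant recurrent, (2) platinum-sensitive recurrent and (3) non-recurrent patients. The endpoint sentence is "The primary performance endpoint is histopathologic evidence of tumor cell capture (see 2.5", and the derivation it points to in SAP 2.5 scores capture as present when "Tumor cell infiltration for at least one device is >0 in a patient". Neither carries a recurrence condition.

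For the secondary endpoint, focalization, SAP 2.4.6 keeps the protocol's denominator: "The secondary performance endpoints are the percentages of recurrent patients with disease focalization scores of". It also asks for groups (1) and (2) combined, and so does SAP 2.4.7 ("Disease Focalization will be also analyzed using the 3 sub-populations defined below", followed by the combined group). Table 59 in SAP 4.1 reports capture on the As-Treated population "with sub-analysis of histological evidence of tumor cell capture by device location and recurrence status", without listing the status categories.

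SAP section 1 describes its own role: "This SAP provides additional details concerning the statistical analyses outlined in the protocol". It announces no change of endpoint.

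**The concern.** A programmer following the SAP as written would report the As-Treated capture rate as the primary performance result. A reader of Protocol 10.3 would expect the rate among recurrent patients.

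The two answer different questions. The recurrent rate asks how often the device captured cells in patients whose disease came back. The As-Treated rate mixes those patients with patients who did not recur, so it also depends on how many recur and on capture in the others, which is unknown.

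Capture has no hypothesis test, so the estimate and its interval are the whole primary performance result. In an open single-arm study meant to support CE-marking, having two candidate primary rates leaves room to choose between them after the data are seen.

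**Working it through.** The plan gives no sample size, power or target for capture, so there is no figure of its own to reproduce on this point. The n = 20 is sized for the safety endpoint and does not bear on it.

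**1. The texts side by side**

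| | Capture (primary) | Focalization (secondary) |
|---|---|---|
| Protocol 10.3 | Recurrent patients, As-Treated set | Recurrent patients, As-Treated set |
| SAP text | As-Treated set, no recurrence condition | Recurrent patients, As-Treated set |
| SAP sub-groups | (1), (2), (3) | (1), (2), (3), plus (1)+(2) combined and overall |

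SAP 2.5 defines platinum-sensitive as recurrent and not platinum-resistant. Groups (1) and (2) therefore add up to all recurrent patients, provided nothing is missing. A recurrent patient without a chemotherapy date could fall in neither group, because SAP 2.5 sets a derived item to missing when an input is missing.

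**2. Size of the gap**

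Let r be the recurrent share of As-Treated patients, and c_R and c_N the capture rates in recurrent and non-recurrent patients.

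- Protocol rate = c_R
- SAP rate = r·c_R + (1 − r)·c_N
- Gap = (1 − r)·(c_R − c_N)

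**3. A range for r**

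Protocol 1.5 gives about 40–50% progressing at 12 months and nothing at 18 months. Assuming exponential times to progression:

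- 40% at 12 months: r = 1 − 0.6^1.5 = 0.535, or 10.7 of 20; 1 − r = 0.465
- 50% at 12 months: r = 1 − 0.5^1.5 = 0.646, or 12.9 of 20; 1 − r = 0.354

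Each 10-point difference between c_R and c_N therefore shifts the SAP rate by 3.5 to 4.6 points. At 80% against 0% capture the gap is 0.8 × 0.354 = 28 points to 0.8 × 0.465 = 37 points.

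**4. Illustrations**

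The lower bound is the exact one-sided 90% (Clopper–Pearson) limit, the 10th percentile of Beta(x, n − x + 1). All capture counts are assumed, with 20 As-Treated patients. In the first three rows no non-recurrent patient shows capture.

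| Recurrent of 20 | Protocol rate (lower bound) | SAP rate (lower bound) |
|---|---|---|
| 11 | 9/11 = 82% (58.5%) | 9/20 = 45% (29.3%) |
| 13 | 10/13 = 77% (55.6%) | 10/20 = 50% (33.8%) |
| 10 | 8/10 = 80% (55.0%) | 8/20 = 40% (24.9%) |
| 10, equal capture in both groups | 8/10 = 80% (55.0%) | 16/20 = 80% (63.9%) |

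The formula agrees with the first row: (9/20) × (9/11) = 0.368, and 81.8% − 45.0% = 36.8 points. The last row shows that the gap vanishes when capture does not depend on recurrence.

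**The case against.** The strongest reply is that SAP 2.4.5 is silent on the denominator and does not change it. Protocol 10.3 also names the As-Treated set beside a recurrent-patient endpoint, and SAP 2.4.6 does the same for focalization, so naming As-Treated does not by itself settle who is counted. The SAP's endpoint sentence closely follows Protocol 4.1.2. Tables 84–87 and 101 use the same recurrence-status label as Table 59, and for those analyses the text requires the combined group, so Table 59 may well have been meant to show it. On this view the omission is a drafting slip.

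It may well be a slip, but the silent reading does not fit a section that lists non-recurrent patients as a sub-population of the primary analysis. A table label neither makes a pooled line primary nor calls for its interval, and the Type 2 layout assigned to Table 59 shows only counts and percentages.

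Four points on the other side stand:

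- No threshold or decision rule is attached to capture, and the pooled result can be recovered from Listings 22 and 26.
- The capture counts are invented, and the large gaps need little or no capture in non-recurrent patients.
- Recurrence in the SAP rests on the reason for device removal, which need not match published progression rates, so the range for r is only a guide.
- A denominator of 20 assumes histology for everyone. The SAP computes percentages on non-missing values, so non-recurrent patients without explant histology could drop out and narrow the gap. If five did (an assumption), 9/20 = 45% would become 9/15 = 60%.

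**Conclusion.** The inconsistency is real and concerns a primary endpoint. Protocol 10.3 is the only protocol section that fixes a denominator for capture. Following the SAP as written reports a different quantity as primary and never calls for the protocol's quantity with its interval.

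The textual conflict needs no assumption; its numerical size does. It depends on the recurrent share, taken as 54–65% under the exponential extrapolation, and on how far capture differs between the two groups. It ranges from zero if capture is equal to roughly 28–37 points if capture is 80% in recurrent patients and nil in the others.

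No stated sample size, alpha level or decision rule is affected. This should be fixed, but it does not invalidate the design.

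**What to change.** In SAP 2.4.5, state that the primary performance estimate is the capture rate among recurrent As-Treated patients, groups (1) and (2) combined, with its exact one-sided 90% interval. Label the all As-Treated, by-location and separate-group results as supportive. Add the pooled recurrent line to Table 59, with a place for the interval. Keep the SAP 2.5 definition of recurrent.

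As a precaution on which the conclusion does not rest, finalise the list of other removal reasons that count as recurrence before core-laboratory results are seen. The recurrent denominator depends partly on that classification by the sponsor, whereas the As-Treated rate does not.

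The cost is two sentences, one table line with its interval, and a date. No new data are needed, and neither the focalization denominator nor the Kaplan–Meier censoring rule changes. The downside is precision: at 80% capture the lower bound is 55.0% with 10 patients, against 63.9% with 20.

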2.4.6. Secondary analysis

Secondary analysis of safety will be performed on the ITT population and the As-Treated populations.

STATISTICAL ANALYSIS PLAN

Secondary safety endpoints include incidence of other device-related adverse events and all other adverse events long-term. Patients will be evaluated by physical examination, CT scan, ultrasound, and biomarker cancer antigen CA-125.

A medical coding will be done on the adverse events using the MedDRA dictionary. All adverse events (AEs) will be categorized by system organ class (SOC) and preferred term (PT). A complete description will be done for the following AEs:

- Total number of AEs/SAEs and corresponding number and percentage of patients
- Total number of device-related AEs/SAEs and corresponding number and percentage of patients
- Total number of unanticipated device-related AEs/SAEs and corresponding number and percentage of patients
- Total number of procedure-related AEs/SAEs and corresponding number and percentage of patients
- Total number of device deficiencies and corresponding number and percentage of patients
- The overall mortality rate will also be presented

Secondary analysis of performance will be performed on the As-Treated population.

Secondary performance endpoints include semi-quantitative scoring of disease focalization based on direct visual assessment, CT scan and ultrasound at the time of device removal. In addition, a microscopic assessment will be performed during explant, including cytological assessment of any ascites present, cytological assessment of peritoneal washings, if indicated, and a minimum of two (2) peritoneal biopsies from designated locations, if indicated.

The secondary performance endpoints are the percentages of recurrent patients with disease focalization scores of: 1) I, 2) I or II, 3) I, II or III, and 4) I, II, III or IV. This analysis will be also performed using the 3 sub-populations defined below ((1), (2), (3)), and using the populations (1) and (2) combined and overall.

The secondary performance endpoints will be assessed with exact one-sided 90% confidence intervals.

2.4.7. Device Removal

Descriptive statistical data will be used to draw up a recapitulation of the device removal details at the time of the removal operation.

The following data will be presented on the As-Treated population on patients number:

- Duration until device removal (days), Reason for removal, All devices removed (Yes/No), The number of devices removed if No. Duration until device removal (days) if the reason for removal is recurrence.
- The time to recurrence will be described using a Kaplan Meier curve. Patients lost to follow-up before the removal will be censored at the date of last follow-up. Patients who have removal for another reason than recurrence before the 18 months will be censored at the date of the removal.
- Disease Focalization: Disease focalization score, Modalities used for the assessment of disease focalization, If a peritoneal wash performed, were malignant cells present (Yes/No)
Disease Focalization will be also analyzed using the 3 sub-populations defined below ((1), (2), (3)), and using the populations (1) and (2) combined and overall.
- Adverse Event: New adverse event(s) occur during removal procedure (Yes/No)
- Cytology (Done with final device removal): Where ascites present (Yes/No), Were malignant cells present in the ascites (Yes/No), Was a peritoneal wash performed (Yes/No), From which area was the wash obtained if "Yes", Were malignant cells present in the peritoneal wash.

	STATISTICAL ANALYSIS PLAN	MTRAP_SAP_v2.0_FINAL redacted.docx
		MTRAP Page 14/15

- Biopsies (Done with final device removal): Biopsy location, Biopsy taken (Yes/No), Is visible tumor present (Yes/No), Is microscopic disease present (Yes/No)

If Biopsy location is Adhesive bands, abnormally scarred areas or Retroperitoneum the further details given will be described by the mean of listing.

The following data will be presented on the As-Treated population on devices number:

- Location of Device, Attachment of the device to the surrounding tissues
- Assessment of device removal: Ease of locating M-Trap device, Did the M-Trap device remain securely fixed in its original location, Ease of removing M-Trap device, Endobag used, Trocar size (mm)
- Core Lab: Device(s) sent to the core laboratory (Yes/No), the Reasons and the Location if No
- Data Entered by Core Lab: Device size (Length (mm) and Width (mm)), Immunohistochemistry (CD3, CD20, CD68, CKAE1/AE3, CK7, ER, P53, WT1 (Key: (0)=nil, (1)=mild, (2)=moderate, (3)=marked)), CD31 and D240 (Yes/No), Tumor cell infiltration (%), Gross photo taken (Yes/No), Images from a microscope obtained (Yes/No).

